NCT03751020

Title of Research Project: Development and preliminary trial of a
brief, portable health intervention for rural sexual minority
emerging adults

SAP Date 7.29.2019

Development and Preliminary Trial of a Brief, Portable Health Intervention for Rural Sexual Minority Emerging Adults

Statistical Analysis Plan

We will use hierarchical linear modeling to evaluate whether SA or EW demonstrate greater decreases from baseline in depressive symptoms, suicidality, substance use, and HIV risk behaviors, at post-intervention and 3-mo. follow-up relative to control participants. Level 1 will include time and the Level 2 variables will include intervention condition and possible covariates such as demographic and psychosocial variables. We will conduct “intent-to-treat” analyses in which all cases are analyzed and multiple imputation is used to estimate follow up data for treatment non-completers. Evidence for a significant main effect for improved outcomes will provide pilot data to justify a larger RCT examining the longer-term effectiveness (e.g., 6- and 12-month follow-ups) of one or both of our writing interventions. Analyses will also explore the degree to which social support, gender, baseline health risk, and identity centrality moderate intervention effects. Although we are likely not fully powered to detect mediation, our design and sample size allow us to estimate the size of the direct paths to and from the mediators—estimates that will determine the sample size for a future proposal. However, if the magnitude of the direct paths to and from the mediators are medium to large, as suggested by previous research, we would be sufficiently powered ($1 - \beta = .8$) to use a bias-corrected bootstrap approach to test mediation. Evidence for mediational effects will provide critical new information about mechanisms underlying SA and EW intervention efficacy.

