## **SECTION IV: RESEARCH PLAN**

1. **Statement of Purpose:** State the scientific aim(s) of the study, or the hypotheses to be tested.

*Aim 1 (Conduct elicitation research, phase 1):* 

We will conduct focus groups and structured interviews with 20 rural lesbian, gay, and bisexual (LGB) emerging adults and LGB community leaders in order to create appealing, culturally resonant intervention materials for rural Appalachian LGB emerging adults (aged 18-29 years).

Aim 2: (Use elicitation research findings to adapt interventions, phase 2):

We will interview 10 LGB emerging adults and LGB community leaders to further refine

Expressive Writing (EW), Self-Affirmation (SA), and Control (C) online writing interventions for use among LGB emerging adults in rural Appalachia.

Aim 3: (Intervention feasibility, acceptability, and preliminary efficacy testing, phase 3):

We will examine the feasibility, appeal, and preliminary efficacy of EW and SA interventions relative to control. The primary outcomes of interest will include depressive symptoms, suicidality, substance use, and HIV sexual risk behaviors at the 3-month post-intervention assessment.

2. **Background:** Describe the background information that led to the plan for this project. **Provide references** to support the expectation of obtaining useful scientific data.

Lesbian, gay, and bisexual (LGB) emerging adults (ages 18-29) report significantly greater depression, suicidality, substance use, and HIV risk behaviors than heterosexuals (1,2). These disparities are magnified among LGB emerging adults who live in rural or nonurban areas in the US (3). Indeed, rural LGB emerging adults are more likely to binge drink, use illegal drugs, and report depression than their urban LGB peers (4,5). These disparities are particularly severe in Appalachia, a cultural context characterized by negative attitudes and interpersonal discrimination towards LGBs (6,7), mental and physical health outcomes among the poorest in the nation (8), and limited access to mental and physical health providers (9).

This proposal is designed to adapt and test the feasibility and efficacy of online Expressive Writing (EW) and Self-Affirmation (SA) writing interventions that offer two low-cost, portable vehicles capable of mitigating mental health and behavioral risk disparities among Appalachian LGB emerging adults.

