#### PHASE/AIM 3:

We will recruit 108 Appalachian LGB emerging adults (36 per group) who (i) are aged 18-29, (ii) self-identify as a sexual minority (e.g., lesbian, gay, bisexual, pansexual, queer), (iii) currently live in Eastern Tennessee counties of Washington, Sullivan, Carter, Unicoi, Greene, or Hawkins County, and (iv) have daily personal internet access. Participants will be recruited, screened, and consented for an online writing intervention using Phase 1 strategies. Recruited individuals will be directed to complete a brief online screener gauging eligibility where they will consent to share their information with the research team. Those who consent to the online screener and meet the study eligibility criteria will then receive a call from a research team member who will share additional information about the study and gain consent for study participation. During the consent call, study staff will confirm participant age, contact information (such as phone number and address), and give participants the option to provide a secondary contact. After providing consent, participants will be emailed a link to complete an online baseline assessment (Study Task 1), then randomized to one of the three online writing interventions to be completed daily for three days starting the Monday of the following week (Study Task 2-Study Task 4). Participants will have up to two weeks to complete the three days of writing prompts. If the participant has not begun their first writing day (Study Task 2) within 24 hours of receiving the prompt than they will receive one email reminder per day for three days encouraging them to complete their writing prompt. If they still have not completed their writing prompt by the fifth day, then a research team member will try calling or texting the participant to remind them to complete the task. Upon completion of the first writing day (Study Task 2), the participant will have 24hrs to complete the second writing day (Study Task 3). If the participant does not complete the second writing day (Study Task 3) within 24 hours, then study staff will use the same email, text, and call reminder system as with writing day one (Study Task 2) to encourage them to complete writing day two (Study Task 3). The same communication and reminder protocol will be followed to encourage the participant to complete the third writing day (Study Task 4). Cumulatively, participants will have 14 days to complete the three writing prompts, but participants will not be invited to move on to the second writing prompt without first completing the prompt from writing day one, nor will they be prompted to complete the third writing task without submitting the second writing task. Seven days after completing their final writing task, or seven days after the close of the

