	clusion/Exclusion Cri clusion?	teria: What are the cri	teria used to determine partici	pant inclusion or
Participants in this study will be Appalachian lesbian, gay, and bisexual (LGB) emerging adults who (i) are aged 18-29, (ii) self-identify as a sexual minority (LGBTQ+), and (iii) currently live in Eastern Tennessee counties of Washington, Sullivan, Carter, Unicoi, Greene, or Hawkins County. For Phase/Aim 3, participants must also (iv) and have access to a minimum of 20 minutes per day of personal internet access. (Note: there is no agerestriction for the pre-identified community leaders/stakeholders in Phase 1 and Phase 2.)				
		-	ers have already indicated the on file for the NIH funding app	1.1

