## 4. How was this estimate derived?

15 LGB emerging adults (10 in Phase 1 and 5 in Phase 2) and 10 community leaders (10 in Phase 1, five of whom will repeat in Phase 2) is the estimated number of participants needed to develop and refine the intervention materials before saturation is reached, as per our previous similar intervention development research (e.g., [name] et al., 2013; [name], 2014).

Phase 3 of the project, which aims to recruit 108 participants (36 per each of three conditions: EW, SA, C), is powered primarily to examine feasibility and acceptability. This phase will allow us to determine the preliminary efficacy of the interventions. Our sample size provides sufficient power (1- $\beta$  = .8) to detect intervention effects consistent with effect size estimates identified in a meta-analysis of EW interventions across general population samples in which the average effect size (d) was .47 across physiological, psychological, self-reported health, and health behavioral outcomes. In order to detect an effect of .47 we need 36 participants per group. This sample size will also afford sufficient power (1- $\beta$  = .8) to detect moderation effects found in previous examinations of EW moderation (e.g., social support) (i.e., d = .46 $^{10}$ ), and estimate the direct path to and from the proposed mediators (stress and self-regulation), as secondary aims.

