## **Mental Health and Risk**

Center for Epidemiological Studies -- Depression Scale (CESD), Brief Symptom Inventory (BSI), Beck Anxiety Inventory (BAI), Suicidality, Suicidal Ideation Attributes Scale (SIDAS), Self-Injury, Alcohol Use Disorders Identification (AUDIT), Short Inventory of Problems-Modified for Drug Use (SIP-DU), Sexual Behavior with Main Partner (SB-MP), Sexual Behavior with Casual Partners (SB-CP), Health Care Access and Experiences

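### One linear model of change is planned for every outcome: with zero-heavy scores, its test of moderation by the score's own baseline is unreliable, and the missing baseline adjustment costs power

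*SAP*

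**What the plan says.** The whole SAP is one paragraph. Its model sentence begins "We will use hierarchical linear modeling to evaluate whether SA or EW demonstrate greater decreases from baseline" and covers depressive symptoms, suicidality, substance use and HIV risk behaviours. Time is at level 1; condition and possible demographic and psychosocial covariates are at level 2. No ordinal, count, two-part or transformed model is named, and there is no robust standard error or distribution check. The outcome's own baseline score is not named as a covariate. Missing follow-up is multiply imputed by an unspecified method.

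The protocol (Section IV, Aim 3) makes all four domains primary: "The primary outcomes of interest will include depressive symptoms, suicidality, substance use, and HIV sexual risk behaviors at the 3-month post-intervention assessment". The measures list (Section VI, Mental Health and Risk) includes "Suicidal Ideation Attributes Scale (SIDAS), Self-Injury, Alcohol Use Disorders Identification (AUDIT), Short Inventory of Problems-Modified for Drug Use (SIP-DU" and two sexual-behaviour measures.

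The inclusion criteria admit "emerging adults who (i) are aged 18-29, (ii) self-identify as a sexual minority (LGBTQ+), and (iii) currently live in Eastern Tennessee", plus internet access for Phase 3. No minimum score or behaviour is required.

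On moderation the SAP says: "Analyses will also explore the degree to which social support, gender, baseline health risk, and identity centrality moderate intervention effects". The protocol (Section IV, Specific Aim 3) calls moderation by baseline risk secondary. Neither document says how baseline health risk is scored.

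**The concern.** In a sample not selected for symptoms, many participants may score zero on suicidality, drug-problem and sexual-risk measures. Such scores have a variance that grows with their level. Linear model-based standard errors assume constant variance. In a baseline-by-arm test, the few participants with high baseline scores have both the most leverage and the most noise, so the standard error comes out too small.

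The second issue is separate. A model of decrease from baseline, without adjustment for the baseline score, carries the baseline noise into the treatment contrast.

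At stake are a moderation finding that may be an artefact, and power in a trial with only 36 per arm.

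**Working it through.** **Inputs from the documents.** Three arms: "We will recruit 108 Appalachian LGB emerging adults (36 per group". Three occasions (baseline, post-intervention, 3 months). Instruments, entry criteria and moderators as above.

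**Assumed, because the documents do not say.** Two-sided 5% tests. Complete data. Scores are Poisson with gamma person effects (shape 2 down to 0.5), gamma occasion effects (shape 4 down to 1.5) and 0–50% structural zeros, with mean parameter 4–5. Baseline to 3-month correlation is about 0.45–0.58. Some runs cap the score at 10 or 15.

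**Step 1: the plan's own figure.** The protocol states: "In order to detect an effect of .47 we need 36 participants per group", at 80% power. For two arms, two-sided:

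n per arm = 2(1.96 + 0.84)²/d² = 2 × 7.85/0.2209 = 71.1, or 72 with the t correction.

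At 36 per arm, power is 51%. ANCOVA multiplies n by (1 − r²), and 72 × (1 − 0.71²) = 35.7, so 36 emerges with baseline adjustment and r of about 0.71 (about 0.5 if the two follow-ups are averaged). It also emerges from the one-sample formula, 7.85/0.2209 = 35.5. None of these is stated. This mismatch is a separate issue; it is shown here because it indicates what baseline adjustment is worth.

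**Step 2: change against ANCOVA.** Relative to the follow-up score alone, the variance factor is 2(1 − r) for change and 1 − r² for ANCOVA. At r = 0.45 these are 1.10 and 0.80; at r = 0.58, 0.84 and 0.66.

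**Step 3: why the moderation test is too liberal.** For a slope on baseline x, the true variance is Σ(xᵢ − x̄)²σᵢ² / [Σ(xᵢ − x̄)²]². The model uses σ²/Σ(xᵢ − x̄)². If σᵢ² rises with xᵢ, the second is too small.

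**Step 4: rejection rates with no treatment effect** (36 per arm, 600 trials, nominal 5%). The second and third columns use the same score as moderator; the last three are 2-df tests with other moderators.

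| Zeros, cap | 2 df | EW v control | Other measure, r about 0.4 | Any/none split | Unrelated |
|---|---|---|---|---|---|
| 12%, none | 21% | 17% | 6% | 0% | 6% |
| 37%, none | 41% | 27% | 7% | 1% | 5% |
| 57%, none | 54% | 35% | 11% | 12% | 7% |
| 70%, none | 60% | 40% | 13% | 28% | 5% |
| 37%, 15 | 12% | 10% | 5% | 2% | 5% |
| 57%, 15 | 26% | 17% | 7% | 10% | 6% |
| 70%, 10 | 33% | 22% | 7% | 23% | 5% |

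A normal outcome gives 4%, so the skew is the cause. A top-third split gives 11–22%. Simulations with other generators agree:
- 7–54% zeros: 25–53% (2 df) and 19–35% (one contrast).
- 25–49% zeros, capped at 50 or 15: 27–53% (2 df) and 18–37% (one contrast).
- 49–54% zeros, capped at 50 or 15: 24–33%.

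**Step 5: alternatives for the moderation test, same null.**
- Rank scale: about 5–6%.
- Proportional odds: 4% and 10.8% in two scenarios of one simulation, 5–7% in another.
- HC3 standard errors: about 7–14%.
- log(y + 1): 4% up to 37% zeros, but 14–36% beyond.
- Negative binomial Wald: 11–15%.

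**Step 6: main effect, EW v control at 3 months.** Type I error of the linear model is 3–6% across the simulations. Power at a rate ratio of 0.5, uncapped scores:

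| Zeros | Linear change model | Linear ANCOVA | log ANCOVA | Gain from adjustment |
|---|---|---|---|---|
| 12% | 67% | 91% | 86% | 24 |
| 37% | 40% | 60% | 59% | 20 |
| 57% | 23% | 35% | 36% | 12 |
| 70% | 17% | 20% | 23% | 3 |

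With 7–54% zeros under another generator, change has 17–60%, linear ANCOVA 27–86% and rank ANCOVA 26–84%. The gap between change and linear ANCOVA is thus 27 − 17 = 10 to 86 − 60 = 26 points. Once baseline is adjusted for, leaving the linear scale adds little: log minus linear ANCOVA is −5, −1, +1 and +3 points.

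**The case against.** **The size is assumed.** This stands. Neither document gives a mean, SD or share of zeros, and instrument detail is left to an appendix. A reader might infer that about a quarter to a third of trials would show false moderation. That band lies inside the range above but reflects one choice of zeros, cap, degrees of freedom and moderator, so the documents do not support it as a property of this plan.

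**The moderator may be something else.** This also stands. With a different risk measure the inflation is small, and with an any/none split it is absent in some scenarios. But the SAP leaves the term undefined, so the outcome's own baseline score remains permitted.

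**The SAP does not forbid baseline adjustment.** True: psychosocial covariates are possible. But the outcome's baseline score is not named, and the stated target is decrease from baseline.

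**Linearity itself might be blamed for the power loss.** A reader might infer this and call for a count model. The figures do not support it at a rate ratio of 0.5. The plain negative binomial Wald test also has 10–19% main-effect type I error at this sample size, so its apparent gain is partly spurious. What remains is a larger effect: at a ratio of 0.35, proportional odds reached 53–54% against 35–47% for linear ANCOVA.

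**Moderation is exploratory and secondary.** This stands and limits the consequence. A reader might infer that spurious moderation would be carried into the next trial. The SAP says only that a main effect would justify that trial and that mediator-path estimates would set its size.

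**Conclusion.** The concern holds in a limited form. Under assumed skewed, zero-heavy scores (about 7–70% zeros), 36 per arm and no treatment effect, the model-based linear test of moderation by the outcome's own baseline score rejects in roughly 10–60% of trials at a nominal 5%. With a different, moderately correlated risk measure the rate is about 5–13%.

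False applies here to the no-effect case only. If treatment multiplies scores, an interaction on the mean-difference scale is real.

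A reader might infer that the primary comparisons are invalid. They are not: main-effect type I error stays near 5%. They do lose about 10–26 points of power at a rate ratio of 0.5 in most scenarios, and less when zeros reach about 70%. That loss comes mostly from the missing baseline adjustment.

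No single replacement is shown to be uniquely right. The proportional-odds interaction reached 10.8% in one scenario, and an ordinal mixed model with three occasions, dropout and imputation was not tested.

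**What to change.** In the SAP:

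1. Adjust every outcome model for that outcome's baseline score, or constrain the arms to be equal at baseline.
2. For the suicidality, drug-problem and sexual-risk scores, and for AUDIT if it proves similarly skewed, test moderation by baseline risk on an ordinal or rank scale or by permutation, not with model-based linear standard errors. HC3 reduces the inflation but does not remove it.
3. Define baseline health risk (which score, continuous or split) and the scale on which moderation is judged.
4. Impute these scores by predictive mean matching or an ordinal method.
5. Label moderation results exploratory wherever they are reported.

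The cost is SAP wording and slightly more analysis. Moderation effects for these outcomes would no longer be expressed as mean differences. Recruitment and data collection do not change.

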**Specific Aim 1:** Conduct elicitation research with 20 Appalachian LGB emerging adults and LGB community leaders in order to develop effective intervention materials and stress targets. Participants will be asked to describe the type and frequency of sexual minority stressors faced by LGB emerging adults in their region (to create EW prompts and SA vignettes) and strategies to enhance the LGB-affirmative look-and-feel of the Phase 3 online platform.

**Specific Aim 2:** Present Specific Aim 1 results to 10 Appalachian LGB emerging adults and LGB community leaders to refine the EW prompts and SA vignettes and the LGB-affirmative, culturally relevant look-and-feel of the online platform. Identify, with these leaders, the most effective venues and materials for participant recruitment and retention, and identify the most effective modalities for future intervention dissemination.

**Specific Aim 3:** Pilot test feasibility and efficacy of writing interventions. 108 Appalachian LGB emerging adults will be randomized to complete one of three writing interventions (EW, SA, Control). They will be asked to complete outcome measures (depressive symptoms, suicidality, use of alcohol and illicit drugs, HIV risk behavior) and measures of proposed mediators (self-reported and biological stress, behavioral and emotional self-regulation) and moderators (e.g., social support,

identity centrality) at baseline, post-intervention, and three-month follow-up. In addition, structured interviews with 15 intervention participants will be used to refine study procedures as we scale up this intervention for a future RCT. Primary analyses will determine efficacy; secondary analyses will determine the moderating role of social support, gender, and other psychosocial factors (e.g., baseline risk) and estimate the effect sizes of the mediators of intervention efficacy for use in a subsequent RCT to determine the long-term efficacy and mechanisms of these interventions.

Despite evidence indicating that mental and physical health disparities are most severe among LGB emerging adults living in rural areas of the U.S., there are currently no evidence-based psychological interventions designed to mitigate sexual minority stress effects among this population (19). The proposed culturally-relevant, theory-based interventions are poised to reduce this gap and, therefore, address one of the most pressing public health goals of the U.S. Department of Health and Human Services (20, 21).

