We will conduct focus groups with 20 Appalachian LGB emerging adults and LGB community leaders to create culturally relevant intervention materials that can be feasibly implemented in rural contexts. We will utilize elicitation research findings from Aim 1 to adapt Expressive Writing (EW), Self-Affirmation (SA, and Control (C) online writing interventions for use among rural LGB emerging adults in rural Appalachia. Interviews with 10 Appalachian LGB emerging adults and LGB community stakeholders will additionally inform the intervention content as well as recruitment strategies. Finally, we will examine the efficacy of EW and SA relative to C. The primary outcomes of interest will include depressive symptoms, suicidality, substance use, and HIV risk behaviors at 3-month post-intervention.

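### The SAP asks about change from baseline relative to control, but writes no condition-by-time term or baseline adjustment and cites a 'main effect' as the supporting result; a baseline-adjusted contrast would be clearer and more precise

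*SAP*

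**What the plan says.** The SAP is a single paragraph. Its question is to "evaluate whether SA or EW demonstrate greater decreases from baseline in depressive symptoms, suicidality, substance use, and HIV risk behaviors", at post-intervention and at 3 months, compared with control. The model is a hierarchical linear model: "Level 1 will include time and the Level 2 variables will include intervention condition and possible covariates such as demographic and psychosocial variables". The paragraph does not write a condition-by-time (cross-level) term, does not say whether time is linear or categorical, and does not name the baseline outcome as a covariate. Baseline level enters only as baseline health risk, an exploratory moderator. The result offered in support of a further trial is worded: "Evidence for a significant main effect for improved outcomes will provide pilot data to justify a larger RCT".

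The protocol supplies the context:

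- Section IV, item 1 (Aim 3) fixes the time point: "The primary outcomes of interest will include depressive symptoms, suicidality, substance use, and HIV sexual risk behaviors at the 3-month post-intervention assessment". Section IV, item 3 (Research Plan) repeats it.
- Section IV, item 2 (Specific Aim 3) separates efficacy from moderation: "Primary analyses will determine efficacy; secondary analyses will determine the moderating role of social support, gender, and other psychosocial factors".
- Phase/Aim 3 gives the order of events. Participants "complete an online baseline assessment (Study Task 1), then randomized to one of the three online writing interventions", so the baseline score is measured before allocation.
- Section V, item 4 says that Phase 3 "is powered primarily to examine feasibility and acceptability".

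**The concern.** A question about change from baseline relative to control is a condition-by-time question. A main effect of condition, in the usual sense, is a different quantity: the difference between arms averaged over every visit in the model, including the visit before anyone was treated. The SAP asks the first and names the second.

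Two things are at stake. First, the test named should be the test that answers the question, and the SAP's one paragraph is the only model specification in the documents. Second, even if a change-from-baseline test is meant, the plan does not say that it will adjust for the baseline score. That gives up precision at no saving, because the score is collected anyway. With 36 per arm the loss is noticeable, and the efficacy result is meant to inform whether a larger trial is worthwhile.

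**Working it through.** **Inputs from the documents.** 36 per arm and d = .47 (Protocol, Section V, item 4); three assessments, at baseline, post-intervention and 3 months (Protocol, Specific Aim 3).

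**Assumptions, not in the documents.** Continuous outcome with SD 1 at each visit; no difference at baseline and .47 at both follow-ups; two-sided .05; the same correlation ρ between any two visits, shown at .3, .5 and .7; complete data.

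**The plan's own figure.** The protocol says 36 per group gives 80% power for d = .47. A two-sided two-sample t test at one visit gives 50% at 36 per arm and needs about 72 per arm for 80%. The 36 is therefore not reproduced by that test. This is a separate matter, and nothing below depends on it.

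**Variance of each contrast, per person**

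- Change at 3 months: 2(1 − ρ) = 1.40 / 1.00 / 0.60.
- Baseline-adjusted, 3 months: 1 − ρ² = 0.91 / 0.75 / 0.51.
- Change, mean of both follow-ups: 1.5(1 − ρ) = 1.05 / 0.75 / 0.45.
- Baseline-adjusted, mean of both follow-ups: (1 + ρ)/2 − ρ² = 0.56 / 0.50 / 0.36.
- Literal main effect (mean of all three visits): (1 + 2ρ)/3 = 0.53 / 0.67 / 0.80.

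The effect is .47 for the first four. For the literal main effect it is (0 + .47 + .47)/3 = .313, two thirds of .47.

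**Power.** Noncentral t with 2 × 36 − 2 = 70 degrees of freedom and noncentrality effect / √(2 × variance / 36). For example, adjusted at 3 months with ρ = .5: .47 / √(2 × 0.75 / 36) = 2.30, giving 62%.

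| Contrast, one active arm v control | ρ = .3 | ρ = .5 | ρ = .7 |
|---|---|---|---|
| Change, 3 months | 38% | 50% | 72% |
| Baseline-adjusted, 3 months | 54% | 62% | 79% |
| Change, mean of both follow-ups | 48% | 62% | 83% |
| Baseline-adjusted, mean of both follow-ups | 75% | 79% | 91% |
| Literal main effect, all three visits | 44% | 36% | 31% |

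**Gain from baseline adjustment, like for like**

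- At 3 months the variance ratio, adjusted to change, is (1 − ρ²) / [2(1 − ρ)] = (1 + ρ)/2 = .65 / .75 / .85, a cut of 35 / 25 / 15%.
- Averaged over both follow-ups the ratio is (1 + 2ρ)/3 = .53 / .67 / .80, a cut of 47 / 33 / 20%.

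**Across the two time choices.** The adjusted 3-month contrast and the unadjusted two-visit change have equal variance when 1 − ρ² = 1.5(1 − ρ), that is, at ρ = .5. Above that, the unadjusted two-visit change has slightly more power (83% v 79% at ρ = .7).

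**The case against.** The strongest reply is that the SAP's opening question already fixes the test. Listing time at Level 1 and condition at Level 2 is common shorthand for condition predicting the time coefficient, and the protocol's contrast between efficacy and moderation suggests that 'main effect' just means the overall treatment effect. This largely stands. The term is unwritten, not excluded. A reader might infer that the trial will test an effect averaged over baseline; the documents do not support that, and the 44/36/31% row prices only the literal wording.

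A second reply is that what remains is efficiency, not validity. That stands too. Change from baseline is unbiased under randomisation, and the unnamed covariates could include the baseline score. But the gain from adjustment holds at every correlation shown, at either time choice, and needs no new data.

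Third, the case should not be priced at 3 months alone, because the SAP names both follow-ups. This is correct: set against unadjusted change averaged over both visits, the adjusted 3-month contrast gains nothing at ρ = .5 and loses about 5 points at .7. Adjustment wins clearly only when the same visits are compared.

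Fourth, a reader might take the supporting sentence as a go/no-go rule, or as success on any outcome in any arm. The SAP states neither. It speaks of pilot data that would help to justify a further trial, and Phase 3 is sized mainly for feasibility and acceptability.

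**Conclusion.** The point holds as an improvement in precision and clarity. The SAP's question, its listed terms and its named supporting result do not line up, and no baseline-outcome adjustment is stated although the score predates randomisation. On the natural reading, adding the adjustment raises power by about 16/12/7 points at 3 months (54/62/79% less 38/50/72%) and by about 26/17/7 points for the two-visit average (unrounded 74.8/79.4/90.6% less 48.4/62.2/83.4%).

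The sizes depend on the assumed correlations, on a continuous outcome, and on d = .47, a meta-analytic average for EW that is applied here to SA as well. Skewed suicidality or sexual-risk measures, or missing data, would change them. The mismatch between question and named test does not depend on these assumptions.

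The stronger inference, that the literal main effect is always the weakest choice, also fails: at ρ = .3 it has 44% power against 38% for unadjusted 3-month change.

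**What to change.** In the SAP, replace 'main effect' with two condition-by-visit contrasts, EW v control and SA v control. Treat visit as categorical, and either constrain baseline means to be equal across arms or enter the baseline score as a covariate. Take the 3-month contrast as primary, in line with Section IV, items 1 and 3 of the protocol, and report the baseline-adjusted average of both follow-ups beside it.

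The cost is a few sentences of SAP text and a few lines of model code, with no new data. The downside is that the 3-month contrast leaves out the post-intervention visit, so above a correlation of about .5 it has slightly less power than an unadjusted change averaged over both visits; reporting the adjusted average as well recovers that information. Because the SAP is dated 7.29.2019, after the June 2019 end expected in Section II, item 1 of the protocol, the change should be dated and should state whether outcome data by arm had already been seen.
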